#### **3.5.1.1 Overall Safety Assessment**

The analysis strategy of safety results is summarized in [Table 1](#). The overall safety evaluation will include a summary by intervention group of the number and percentage of participants with at least one AE, SAE, drug-related AE, drug-related SAE, Grade 3 to 4 AE, drug-related Grade 3 to 4 AE, discontinuation from study intervention due to an AE; and AE resulting in death. Point estimates and 95% CIs for the differences between each MK-8527 group and placebo in the percentages of participants with the event will be provided using the M&N method [Miettinen, O. and Nurminen, M. 1985].

For continuous safety measures, such as change from baseline in laboratory values, summary statistics for baseline, on-treatment, and change from baseline values will be provided by treatment group.

The number and percentage of participants with specific AEs will also be provided.

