1 PROTOCOL SUMMARY

1.1 Synopsis

Protocol Title: A Phase 2a, Double-Blind, Placebo-Controlled Study to Evaluate the Safety, Tolerability, and Pharmacokinetics of Oral MK-8527 Once Monthly in Participants at Low-Risk for HIV-1 Infection

Short Title: Safety and Pharmacokinetic Study of Oral MK-8527 QM in Participants at Low-Risk for HIV-1 Infection

Acronym: Not applicable

Hypotheses, Objectives, and Endpoints:

There are no hypotheses to be tested in this study.

The following objectives will be evaluated in adults at low-risk of human immunodeficiency virus type 1 (HIV-1) infection.

Primary Objective	Primary Endpoint
To evaluate the safety and tolerability of MK-8527 once monthly (3 mg, 6 mg, and 12 mg) during treatment and through the last follow-up visit.	Adverse events Adverse events leading to discontinuation of study intervention
Secondary Objectives	Secondary Endpoints
To characterize the plasma pharmacokinetic profile of MK-8527 once monthly (3 mg, 6 mg, and 12 mg).	MK-8527 AUC _{0-last} and C _{max}

Overall Design:

Study Phase	Phase 2
Primary Purpose	Treatment
Indication	HIV infection
Population	Adults at low-risk for HIV-1 infection
Study Type	Interventional
Intervention Model	<<Intervention Model>> This is a multi site study.
Type of Control	Placebo

Study Blinding	Double-blind
Blinding Roles	Participants or Subjects Sponsor Investigator
Estimated Duration of Study	The Sponsor estimates that the study will require approximately 58 weeks from the time the first participant (or their legally acceptable representative) provides documented informed consent until the last participant's last study-related contact.

Number of Participants:

Approximately 350 participants will be randomized in a 2:2:2:1 ratio to 1 of 4 intervention groups: Group 1: MK-8527 (3 mg), N=~100; Group 2: MK-8527 (6 mg), N=~100; Group 3: MK-8527 (12 mg), N=~100; Group 4: placebo, N=~50.

Intervention Groups and Duration:

Arm Name	Intervention Name	Unit Dose Strength(s)	Dosage Level(s)	Route of Administration	Regimen/ Treatment Period	Use
Group 1	MK-8527	3 mg	3 mg QM	Oral	Day 1 to Week 20	Test Product
Group 1	Placebo	0 mg	0 mg QM	Oral	Day 1 to Week 20	Placebo
Group 2	MK-8527	3 mg	6 mg QM	Oral	Day 1 to Week 20	Test Product
Group 2	Placebo	0 mg	0 mg QM	Oral	Day 1 to Week 20	Placebo
Group 3	MK-8527	3 mg	12 mg QM	Oral	Day 1 to Week 20	Test Product
Group 4	Placebo	0 mg	0 mg QM	Oral	Day 1 to Week 20	Placebo

QM=once monthly.

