If a participant discontinues study intervention before the final dose at Week 20, the EOT visit (Visit 11) should be performed in place of the next study visit. If a participant discontinues study intervention and also withdraws from the study before the final dose at Week 20, then only the EOT visit (Visit 11) should be performed in place of the next study visit. If a participant receives the final Week 20 dose of study intervention and then withdraws from the study, an “Early Withdrawal From Study” visit should be performed as the final study visit as outlined in Section 1.3.2 of the SoA.

8.11.3.1 Management of Participants with Specified Decreases in Total Lymphocyte Count or CD4+ T-cell Counts

Participants discontinued from study intervention (prior to the final dose at Week 20) due to confirmed decreases in total lymphocyte count or CD4+ T-cell count (Section 7.1 and [Table 3](#)) should undergo assessments for the EOT visit (Visit 11) as specified in the SoA in Section 1.3.1. To meet the protocol-defined discontinuation criteria, participants must have a confirmed total lymphocyte count or CD4+ T-cell count that indicates a specified decrease on 2 consecutive measurements 1 to 4 weeks apart ([Table 3](#)). Note: The time frame for confirmation of decreases in total lymphocyte count or CD4+ T-cell count may be extended in the setting of intercurrent illness, immunization, or study intervention dosing interruptions (due to missed study visits). Allow approximately 4 weeks following resolution of illness, immunization, or study intervention dosing interruptions before collecting the confirmation sample to allow for evaluation of a potential other causal effect. Consult with the Sponsor prior to discontinuation if the investigator believes there is an alternative explanation for the result (eg, COVID-19).

After discontinuation from study intervention, participants should continue to be followed in the study, by completing the follow-up visits as outlined in the SoA in Section 1.3.1.

Total lymphocyte counts and CD4+ T-cell counts will also be monitored during follow-up (after last dose at Week 20). If a participant has a confirmed decrease in total lymphocyte count or CD4+ T-cell count as per Section 7.1, [Table 3](#), after the last dose at Week 20, participants should continue to be followed in the study, by completing the follow-up visits as outlined in the SoA in Section 1.3.1.

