8.11.6 Follow-up Period

During the 8-week blinded follow-up period, all participants will complete 3 monthly follow-up visits: Follow-up Day 1, Follow-up Week 4, and Follow-up Week 8. PBMC Subset participants will have 1 additional follow-up visit at Follow-up Week 6.

The follow-up visits represent different study day/weeks for a participant that completes the final Week 20 dose and a participant that discontinues study intervention prior to Week 20, as outlined below.

A participant that completes the final Week 20 study intervention dose will return to the site for follow-up visits based on the following:

- **Visit 12/Follow-up Day 1 (all participants):** this visit should be completed ~24 hours after the Week 20 study intervention dose; PK samples must be collected 24 hours (± 6 hours) after the Week 20 dose.
- **Visit 13/Follow-up Week 4 (all participants):** this visit should be completed 24 weeks (± 7 days) from the Day 1 (Visit 2).
- **Visit 14/Follow-up Week 6 (PBMC Subset only):** this visit should be completed 26 weeks (± 2 days) from the Day 1 (Visit 2).

- **Visit 15/Follow-up Week 8 (all participants):** this visit should be completed 28 weeks (± 7 days) from the Day 1 (Visit 2).

A participant that discontinues study intervention prior to the Week 20 dose, will return to the site for follow-up visit based on the EOT (Visit 11) date:

- **Visit 12/Follow-up Day 1 (all participants):** this visit should be completed ~ 24 hours after the EOT visit (Visit 11).
- **Visit 13/Follow-up Week 4 (all participants):** this visit should be completed 4 weeks (± 7 days) from the EOT visit (Visit 11).
- **Visit 14/Follow-up Week 6 (PBMC Subset only):** this visit should be completed 6 weeks (± 2 days) from the EOT visit (Visit 11).
- **Visit 15/Follow-up Week 8 (all participants):** this visit should be completed 8 weeks (± 7 days) from the EOT visit (Visit 11).

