#### **3.3.1 Safety Endpoints**

The primary safety assessment will include all accumulated safety data through the last follow-up visit. AEs leading to discontinuation from study intervention are assessed until Week 20 (last dose received). Safety and tolerability will be assessed by clinical review of all relevant parameters including AEs and laboratory test results.

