### **3.7 Multiplicity**

No multiplicity adjustment is planned for this study.

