### 3.8 Sample Size and Power Calculations

The sample size of this study will allow for the accumulation of approximately 150 person-years of safety data on MK-8527.

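### Observation time depends on stopping, yet adverse events are compared only as crude percentages, so later or other-category events can be understated where more participants stop

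*SAP*

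**What the plan says.** SAP 3.5.1.1 and SAP Table 1 define the overall safety endpoints by the "number and percentage of participants with at least one AE, SAE, drug-related AE" and further categories. The comparison is "Point estimates and 95% CIs for the differences between each MK-8527 group and placebo in the percentages of participants with the event", by the M&N method. On the window, SAP 3.3.1 states: "The primary safety assessment will include all accumulated safety data through the last follow-up visit". The last follow-up visit differs between participants:

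- **Completers.** Protocol 8.11.6 sets the final visit at 28 weeks (±7 days) from Day 1.
- **Early stoppers.** Protocol 8.11.3 says that "the EOT visit (Visit 11) should be performed in place of the next study visit". Under Protocol 8.11.6 an early stopper "will return to the site for follow-up visit based on the EOT (Visit 11) date", and the final visit is 8 weeks (±7 days) after EOT.
- **Unresolved lymphocyte or CD4+ decreases.** Protocol 8.11.3.1 continues roughly monthly visits, with AE assessment, past Follow-up Week 8 until counts recover.

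SAP 3.8 describes the trial's size as "approximately 150 person-years of safety data on MK-8527". SAP 3.11 summarises only the amount of intervention received. Neither document specifies an event rate, a time-to-event estimate, a common cut-off or a summary of observation time by arm.

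**The concern.** A percentage of participants with at least one event is comparable between groups when the groups are watched for similar lengths of time. Here a participant's observation time is set partly by when he or she stops. If one dose group has more stopping, part of its denominator had less time in which to show an event, and the M&N difference takes no account of that. The same would apply, more strongly, to an arm terminated early under SAP 3.6. Safety is the primary objective, and the results are meant to inform the choice of a dose for efficacy studies. A reader of the planned tables could not tell how much of a difference reflects unequal observation.

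**Working it through.** **The plan's own person-time.** With about 100 participants in each of three dose groups and the 6-month period in SAP 3.11: 3 × 100 × 0.5 year = 150 person-years, as stated. Counting all 28 weeks would give 300 × 28/52 = 161.5. The stated figure is therefore planned dosing time.

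**End of observation.** With EOT at the next dosing visit and the final visit 8 weeks later:

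| Last dose | EOT | Last visit |
|---|---|---|
| Day 1 | Week 4 | Week 12 |
| Week 4 | Week 8 | Week 16 |
| Week 8 | Week 12 | Week 20 |
| Week 12 | Week 16 | Week 24 |
| Week 16 | Week 20 | Week 28 |
| Week 20 (completer) | – | Week 28 |

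Twelve weeks is near the short end but is not the floor: in the PBMC Subset an EOT visit at Week 1 gives Week 9. For stops under Protocol Table 3, a first low value at Week 4 must be confirmed 1 to 4 weeks later or at the next scheduled visit. That puts EOT as late as about Week 8 and the last visit at about Week 16, or later without recovery.

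**Assumptions.** The documents give no stopping rate. I take a share *s* of extra stoppers on a dose relative to placebo, the same true hazard in both arms, a constant hazard, and stopping unrelated to AEs. The 28-week incidence *I* is taken from the 10% to 50% range in SAP Table 3.

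**Formulas.** λ = −ln(1 − I)/28. Incidence by week t: p(t) = 1 − exp(−λt). Crude percentage = (1 − s)·I + s·p(t).

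**At I = 30%.** λ = 0.01274 per week and p(12) = 14.2%.

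- All extra stops after one dose, s = 10%: 0.9 × 30 + 0.1 × 14.2 = 28.4%, a drop of 1.6 points.
- The same with s = 20%: 0.8 × 30 + 0.2 × 14.2 = 26.8%, a drop of 3.2 points.
- Stops spread evenly over the five intervals: p(12), p(16), p(20), p(24) and p(28) are 14.2, 18.4, 22.5, 26.3 and 30.0%, with mean 22.3%. At s = 10% the drop is 0.1 × (30 − 22.3) = 0.8 points.

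**Other incidences, all stops after one dose.** At I = 10% the drops are 0.6 and 1.1 points for s = 10% and 20%. At I = 50% they are 2.4 and 4.9 points. A 5% category falls to 4.7% and 4.4%.

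**Stops caused by an AE.** Each such participant already has an event. At I = 30% and s = 10%, if all extra stops are AE-caused, the crude any-AE percentage is 0.9 × 30 + 10 = 37.0%, which is 7.0 points above placebo. If half are AE-caused, 0.9 × 30 + 5 + 0.05 × 14.2 = 32.7%, or 2.7 points above. The difference turns negative only when the AE-caused share f satisfies f(1 − I) < (1 − f)(I − p(12)), that is, f below 0.158/(0.70 + 0.158) = 18%.

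**A terminated arm (illustration).** If its observation averaged 20 weeks, equal hazards would show p(20) = 22.5% against 30%, a gap of 7.5 points.

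**Effect of the remedy.** Under the same assumptions the first-event rate is 100 × 52 × λ = 66.2 per 100 person-years, whatever the value of s.

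**The case against.** A reader might infer that a dose causing more stopping will appear to have fewer adverse events, with the Protocol Table 3 rule making the most affected group the least observed. The documents do not support that as a general statement. All AEs from randomization are reported (Protocol 8.4.1), so AE-driven stops are counted, and the rise shown above is a real excess. Discontinuation due to an AE is itself compared with a 95% CI. Confirmation under Table 3 delays EOT, and unrecovered cases are followed longer.

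Two parts of the concern survive this. An abnormal laboratory value is an AE only if the investigator judges it clinically significant (Protocol 10.3.2), so a Table 3 stop need not be counted as one. And any stopper who does not continue under the recovery rule has less time in which other or later events can be seen.

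The size is also fairly challenged. Stopping after one dose is close to the worst case. If 80% of 28-week events fell in the first 12 weeks, the 1.6-point drop would be 0.1 × 30 × 0.2 = 0.6. The individual-stopping shifts are well below the 20 to 28 points that SAP Table 3 says can be ruled out. The trial tests no hypotheses and relies on clinical review, and the person-years statement does not commit the plan to a rate analysis.

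Finally, the remedies carry assumptions. Exposure-adjusted rates presume a roughly constant hazard and pool dosing with off-drug follow-up, and both remedies presume non-informative stopping. That limits how they are read but does not argue against showing them beside the crude figures.

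**Conclusion.** The concern holds in a limited form. Observation time varies with stopping, from about 12 weeks (somewhat less in a few cases) to 28, and the planned comparison neither adjusts for this nor displays it. Crude percentages can understate later or other-category AEs, SAEs and Grade 3 to 4 events in a group with more stopping, or in an arm terminated early. For any AE, the net direction depends on why participants stop.

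At 30% incidence the understatement is about 0.8 to 1.6 points with 10% extra stopping, and 3.2 points with 20% stopping after one dose. These sizes rest on assumed stopping rates, a constant hazard and stopping unrelated to AEs. The weight is minor to moderate.

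**What to change.** In SAP 3.5.1.1 and SAP Table 1, keep the crude percentages and M&N intervals and add, labelled supplementary:

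1. Observation time by arm, including any time past Follow-up Week 8.
2. For each overall safety endpoint, participants with a first event per 100 person-years at risk, with the rate difference from placebo and its 95% CI. Alternatively, give cumulative incidence with its difference at a fixed time that all completers reach. With the ±7-day window on the final visit, that is Week 27 rather than Week 28.
3. A sentence stating that the rates assume a roughly constant hazard and that both summaries assume non-informative stopping.

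This is a cheap improvement: SAP wording, modest programming and an extra set of table columns. It uses dates already collected and changes nothing in the conduct of the trial.

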4 STUDY DESIGN

4.1 Overall Design

This is a randomized, double-blind, placebo-controlled, parallel-group, multicenter study of oral MK-8527 administered QM in adults who are at low-risk of HIV-1 infection.

Approximately 350 participants will be randomized in a 2:2:2:1 ratio to 1 of 4 intervention groups: Group 1: MK-8527 (3 mg); Group 2: MK-8527 (6 mg); Group 3: MK-8527 (12 mg); and Group 4: Placebo. The screening window is 45 days and participants are allowed to rescreen 1 time (Section 8.11.1.2). The study population composition targets are: $\geq 30\%$ women, $\geq 30\%$ men, $\geq 80\%$ aged ≤ 35 years, and $\geq 30\%$ enrolled in Africa. Randomization will be stratified by sex (female, male) and region (Africa, non-Africa).

Participants will receive a total of 6 oral doses of the assigned blinded study intervention, 1 dose every 4 weeks, starting on Day 1. The final dose will be administered at the Week 20 visit. After the last dose, all participants will complete an 8-week blinded follow-up period.

The primary safety assessment will include all accumulated safety data during the intervention and follow-up period. AEs leading to discontinuation from study intervention will be assessed until Week 20 (last dose received). The Sponsor will perform an ongoing comprehensive review of safety parameters to assess for overall trends and outliers in reported AEs and event toxicities per standard monitoring procedures.

All participants will be evaluated for plasma MK-8527 PK drug levels, and a subset (approximately N=20 participants per intervention group) will be evaluated for MK-8527-TP in PBMC (PBMC Subset).

All participants and the investigators/clinical site personnel directly associated with study conduct will remain blinded to study intervention assignment through the 8-week follow-up period. The siDMC (internal) will be responsible for an interim safety review once 50% of the planned enrollment has reached Week 12 or discontinued from study intervention. Additional meetings of the siDMC may be triggered based on criteria outlined in the SAP/siDMC charter. An unblinded Sponsor team will review PK and safety data on an ongoing basis for the duration of the study. As per amendment 02, all Sponsor personnel except for a blinded medical monitoring team will be unblinded after the last expected Follow-up Week 4 visit, to enable earlier program strategic decision-making by the Sponsor.

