6.3.2 Stratification

Intervention randomization will be stratified according to the following factors:

1. Sex (female, male) (as assigned at birth)
2. Region (Africa, non-Africa)

The effects of study interventions may differ between these subgroups of sex and region. Therefore, sex and region are selected as the stratification factors to ensure that intervention groups will be well-balanced, and the effects of study interventions will not be confounded by those demographic characteristics.

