9.5 Statistical Methods

9.5.1 Statistical Methods for Safety Analyses

Safety and tolerability will be assessed by clinical review of AEs and other relevant parameters, including laboratory test results.

The overall safety endpoints include the number of participants with at least one AE, SAE, drug-related AE, drug-related SAE, Grade 3 to 4 AE, drug-related Grade 3 to 4 AE, discontinuation from study intervention due to an AE; and AE resulting in death.

The safety evaluation will include a summary by treatment group of the number and percentage of participants with each type of AE. For overall safety endpoints, point estimates and 95% CIs for the differences between MK-8527 and placebo in the percentages of participants with events will be provided using the M&N method [Miettinen, O. and Nurminen, M. 1985].

For continuous safety measures, such as change from baseline in laboratory values, summary statistics for baseline, on-treatment, and change from baseline values will be provided by treatment group.

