## 3 ANALYTICAL AND METHODOLOGICAL DETAILS

This section outlines the principal statistical analysis strategy and procedures for the study. Changes to analyses made after the protocol has been finalized, but prior to unblinding, will be documented in an amendment of the SAP and referenced in the CSR for the study. Post hoc exploratory analyses will be clearly identified in the CSR.

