### **3.6 Interim Analyses**

The siDMC will be responsible for an interim safety review. An interim safety analysis will be performed once 50% of the planned enrollment has reached Week 12 or discontinued from study intervention.

Treatment-level results and/or participant-level data from the IA will be provided by the unblinded statistician to the siDMC which consists of Sponsor personnel. Limited additional Sponsor personnel may be unblinded to the treatment-level results of the IAs, if required, to act on the recommendations of the siDMC. The list of individuals who are unblinded with respect to results of IAs will be documented by the unblinded statistician.

The processes by which recommendations and decisions are reached and communicated are documented in the siDMC charter. Individuals who have been unblinded at any level will not be involved in any discussions regarding modifications to the protocol, statistical methods, identification of protocol deviations, or data validation efforts after the IA.

An intervention group may be recommended for early termination due to safety concerns based on the following criteria along with an evaluation of the totality of safety data.

- At least 10% of participants meet discontinuation criteria as detailed in Table 3 of Section 7.1 of the protocol.
- The upper bound of the 95% CI of the difference between the treatment group and the placebo group for the percent change from baseline in lymphocyte count is less than 0.

If at least 10% of participants in a study intervention group meet discontinuation criteria as detailed in Table 3 of Section 7.1 of the protocol, study enrollment will be paused until the siDMC review has been completed.

In addition to the planned IA review, an ad hoc siDMC review will be triggered if  $\geq 10\%$  of all enrolled participants meet the criteria as detailed in Table 3 of Section 7.1 of the protocol at any point during the course of the study. During this time, enrollment in the study will be paused until the siDMC review has been completed.

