#### 3.8.1 Sample Size and Power for Safety Analyses

**Table 2** summarizes the power under various assumptions of the underlying standard deviation to detect the difference in the mean percent change from baseline in lymphocytes. The power is based on the two-sample t-test assuming 100 participants in the MK-8527 group and 50 in the placebo group. For example, if the standard deviation of percent change from baseline in both groups is 20, this study has 81.8% power to detect a difference at least as large as 10%.

Table 2 Power (%) to Rule Out Difference in Mean Percent Change from Baseline  
(With 100 Participants Randomized to MK-8527 and 50 Randomized to Placebo)

Underlying Standard Deviation of Percent Change from Baseline a	Underlying Difference of Mean Percent Change from Baseline in Lymphocytes (MK-8527 - Placebo)					
	-5%	-10%	-15%	-20%	-25%	-30%
10	81.8	>99.9	>99.9	>99.9	>99.9	>99.9
15	48.1	96.9	>99.9	>99.9	>99.9	>99.9
20	29.9	81.8	99.0	>99.9	>99.9	>99.9
25	20.8	63.1	93.1	99.6	>99.9	>99.9
30	15.8	48.1	81.8	96.9	99.8	>99.9

**Table 3** summarizes the differences in the incidence of AEs (MK-8527 minus placebo) that can be ruled out with different power levels and 95% confidence when there are 100 participants in the MK-8527 group and 50 participants in the placebo group. The underlying incidence of AE is assumed to be the same in the MK-8527 group as that in the placebo group. The calculations are based on an asymptotic method proposed by M&N method [Miettinen, O. and Nurminen, M. 1985]. No multiplicity adjustments were made.

Table 3 Difference in Incidence of AEs (MK-8527 Group Minus Placebo) That Can Be Ruled Out With 100 Participants in the MK-8527 Group and 50 Participants in the Placebo Group

Target Power	Difference a in Percentage Points That Can Be Ruled Out with Target Power Assuming the Underlying Incidence of the AE is				
	10%	20%	30%	40%	50%
80	20	23	24	24	23
85	21	24	25	26	25
90	23	26	27	28	27

aThe upper bound of the two-sided 95% confidence interval M&N method [Miettinen, O. and Nurminen, M. 1985] for the difference in AE incidences assuming the incidences are the same.

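### Randomization is stratified by sex and region but the Miettinen-Nurminen AE differences are not; the 95% CIs are valid, yet wider than needed if AE incidence differs by stratum

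*SAP*

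**What the plan says.** Protocol 4.1 stratifies randomization by sex (two levels) and region (Africa or not), which gives four cells. Protocol 6.3.2 gives the reason: "sex and region are selected as the stratification factors to ensure that intervention groups will be well-balanced". It adds that "The effects of study interventions may differ between these subgroups of sex and region".

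The analysis text does not mention these factors. Protocol 9.5.1 describes the AE estimates and their 95% intervals in these words: "differences between MK-8527 and placebo in the percentages of participants with events will be provided using the M&N method". SAP 3.5.1.1 applies this to each dose: "differences between each MK-8527 group and placebo in the percentages of participants with the event will be provided using the M&N method". SAP Table 1 lists eight AE endpoints with a between-group CI and names no strata. The planning figures in SAP 3.8.1 (Table 3) use none either; their only incidence assumption is between arms: "The underlying incidence of AE is assumed to be the same in the MK-8527 group as that in the placebo group". SAP 3.9 prespecifies no subgroup analyses. No reason is given for leaving the stratification factors out.

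**The concern.** When allocation is balanced within strata, differences in AE incidence between strata cannot contribute to the difference between arms. An unstratified standard error still counts that variation. If incidence differs by sex or region, the interval is therefore conservative and wider than the data require.

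AEs are the primary endpoint, and these are the only between-group AE intervals planned; specific AEs receive descriptive statistics only. Each sets about 100 participants against about 50, and at 50% incidence the 95% CI is about 33 points wide. Some of that width may be recoverable at no cost in participants or data.

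**Working it through.** **Inputs from the documents.** Allocation 2:2:2:1, so 100 against 50 for each comparison (Protocol 4.1; SAP 3.8.1); two-sided 95% M&N intervals; four sex-by-region cells.

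**Inputs that had to be assumed.** AE incidence by stratum, the share of each stratum, exact 2:1 balance within strata, and no treatment effect.

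**The plan's own figure.** SAP Table 3 gives 20, 23, 24, 24 and 23 points at 80% power for incidences of 10 to 50%. Under its stated assumption of equal incidence, exact enumeration of the M&N upper bound gives 13.5, 18.1, 21.0, 22.7 and 23.5, so the table does not reproduce. Power to detect a rise from p to p + D gives 19.5, 22.5, 23.8, 23.9 and 23.2. That calculation matches all 15 cells of the table within about 0.5 point. The labelling of Table 3 is a separate matter, and nothing below depends on it.

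**Large-sample size of the effect.** Let w be the stratum share, p the stratum incidence and P the overall incidence.

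- Variance ratio = Σ w·p(1−p) / [P(1−P)]
- Reduction in CI width = 1 − √ratio

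Worked case, equal shares with 30% and 60%: P = 0.45, so P(1−P) = 0.2475. The within-stratum mean is (0.21 + 0.24)/2 = 0.225. The ratio is 0.909, √0.909 = 0.953, and the reduction is about 4.7%.

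With Africa at 30 to 50% of participants and either region higher:

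| Assumed regional incidence | Variance ratio | Reduction in width |
|---|---|---|
| 30% and 50% | 0.958–0.966 | about 2% |
| 30% and 60% | 0.909–0.924 | 4–5% |
| 20% and 60% | 0.833–0.865 | 7–9% |

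**Simulation at the actual sample size.** M&N score intervals, Cochran-Mantel-Haenszel weights, four cells, 3,000 runs. Layout A has 40% Africa and 50% female. Layout B has 30% Africa and 30% female (placebo cells 5, 11, 10 and 24). Mean half-width in points, unstratified then stratified:

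| Scenario | Layout A | Layout B | Change in width |
|---|---|---|---|
| 20-point gap (30% and 50%) | 16.40 → 16.12 | 16.47 → 16.23 | 1.7%; 1.5% narrower |
| 30-point gap (30% and 60%) | 16.59 → 15.93 | 16.60 → 16.02 | 4.0%; 3.5% narrower |
| 40-point gap (20% and 60%) | 16.51 → 15.33 | 16.59 → 15.55 | 7.1%; 6.3% narrower |
| No gap, 50% incidence | 16.59 → 16.60 | 16.59 → 16.60 | 0.1% wider |
| 3% incidence | 7.49 → 7.54 | 7.49 → 7.56 | 0.7%; 0.9% wider |

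A 10-point gap (35% and 45%) gave 0.3% (2,000 runs). At 5% incidence the stratified interval was 0.4 to 0.6% wider, and at 10% it was 0.2 to 0.3% wider. With no events in either arm the interval is −7.18 to 3.72 unstratified and −7.32 to 3.80 stratified.

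**Coverage.** With gaps of 20 to 40 points it was 95.2 to 96.7% unstratified and 94.9 to 95.6% stratified (Monte Carlo standard error about 0.4).

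**Cross-checks.** Simulations of 8,000 trials with four near-equal strata gave widths of 33.2 → 32.0 points for rates of 70/50/50/30% (3.6% narrower) and 33.2 → 30.1 for 80/60/40/20% (9.3% narrower). Unstratified coverage was 95.1 to 98.6% over all scenarios, including more extreme ones. The 70/50/50/30% case has between-stratum variance (0.04 + 0 + 0 + 0.04)/4 = 0.020. The 30-point regional gap has 0.4 × 0.6 × 0.09 = 0.0216 in A and 0.3 × 0.7 × 0.09 = 0.0189 in B, so the two sets of results agree. Adding a 10-point treatment effect left the width ratio at 0.963. A further 4,000-run simulation of both layouts gave the same reductions within 0.1 percentage point, with unstratified coverage of 94.6 to 96.7%.

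**The case against.** The case for leaving the plan alone is reasonable.

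- **Nothing stated is wrong, and no decision turns on the width.** The trial tests no hypotheses, safety is judged by clinical review, and the interim criteria in SAP 3.6 use lymphocyte-based discontinuations and lymphocyte change. This stands, and it is why the point is only an optional improvement.
- **The gain is unproven and usually small.** A 20-point gap moves the half-width by about a quarter of a point, while one placebo participant in 50 is 2 points. The documents do not support a gap of 30 or 40 points. Protocol 6.3.2 speaks of effects that may differ, not of AE rates that do. This stands too.
- **Part of the gain may not survive the collapsing rule.** At the recruitment targets the smallest cell falls below the proposed cut-off. That would lose any gain from a sex difference. For a regional gap, stratifying by region alone still gave 1.6%, 3.5% and 6.1% for 20, 30 and 40 points.
- **The split of endpoints and the cut-off are judgements.** No expected incidence for drug-related AEs is given. If they prove uncommon with no gap between strata, the stratified interval is 0.2 to 1.0% wider at 3 to 10% incidence, which is a very small loss.
- **A weighted difference need not equal the difference of the displayed percentages.** With exact 2:1 balance the weights are proportional to stratum size and the two agree. Small imbalances would separate them slightly.
- **The reading rests on silence.** The SAP never says that the method is unstratified. That supports a clarifying sentence, since otherwise the programmer has to choose.

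**Conclusion.** The concern holds as a minor point of efficiency. The planned intervals are valid, with simulated coverage near or above 95%. If AE incidence differs by region, the stratified form is narrower by about 0.3% for a 10-point gap, 1.5 to 1.7% for 20, 3.5 to 4.0% for 30 and 6.3 to 7.1% for 40. In full width, a 20-point gap gains about half a point on 33, and a 40-point gap gains a little over 2 points. With no gap there is no gain, and for sparse endpoints the stratified interval is slightly wider.

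These sizes rest on assumed stratum rates and shares, balanced allocation within strata, and no treatment effect apart from the one run with a 10-point effect. The gain is possible, not established.

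**What to change.** In SAP 3.5.1.1, state the following:

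- For any AE and any drug-related AE, the difference and 95% CI use stratified M&N, by sex and region, with Cochran-Mantel-Haenszel weights.
- If any sex-by-region cell has fewer than 35 randomized participants over all arms (35 × 1/7 = 5 expected on placebo), stratify by region alone. If a region has fewer than 35, use the unstratified method. These counts are known without unblinding.
- SAEs, drug-related SAEs, Grade 3 to 4 AEs, drug-related Grade 3 to 4 AEs, discontinuation due to an AE, and death keep unstratified M&N.
- A table footnote says that the displayed percentages are crude and the difference is stratum-weighted.

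The SAP already provides the route: "Changes to analyses made after the protocol has been finalized, but prior to unblinding, will be documented in an amendment of the SAP". The amendment should be final before the Sponsor-wide unblinding that follows the last expected Follow-up Week 4 visit (SAP 3.1). Staff who are still blinded should draft it, because an unblinded team that includes a statistician and a programmer reviews data throughout (Protocol 6.3.3). SAP 3.6 also bars unblinded staff from such changes after the interim analysis: "Individuals who have been unblinded at any level will not be involved in any discussions regarding modifications to the protocol, statistical methods". If Sponsor-wide unblinding has already happened, a stratified analysis should be labelled post hoc.

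The cost is a few SAP sentences; the strata are already held in the randomization system. The drawbacks are two interval methods in one table and a collapsing rule that may well apply. At 30% women and 30% Africa, if independent, the smallest cell is 0.3 × 0.3 × 350 = 31.5, or 4.5 on placebo. If the sponsor prefers a single method, one sentence saying that unstratified M&N is intended, and why, would close the gap.
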